4.3. Analysis Sets

4.3.1. Patient Sets

- Non-included patients: all patients who are not included in the study (as recorded in the non-inclusion register).
- Included patients: all patients included in the study.
- Safety analysis set: all patients included in the study who received at least one dose of the documented treatment (the treatment start date must be entered) in the study (targeted therapy or other treatment). If the patient is prevalent, the treatment must

still be ongoing at the time of inclusion in the study and if the patient is incident, the treatment must be started at or after inclusion in the study.

• Reference set (Full Analysis Set): patients included who meet the eligibility criteria and have received at least one dose of the treatment documented during the prospective follow-up period (the treatment start date must be completed and the treatment stop date must be after the date of inclusion if the start date is prior to the date of inclusion) in the study (targeted therapy or other treatment). Patients with no follow-up data will be excluded from this population.

Two treatment groups will be analysed: the "targeted therapy" with two subgroups, everolimus (AFINITOR®) and sunitinib (SUTENT®); and an "other treatments" group with four subgroups: chemotherapy, somatostatin analogs, interferon-alpha and metabolic radiotherapy.

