5.7. Safety

Safety assessment criteria will be used to:

- Treatment discontinuations and reasons for this,
- Adverse events and any complications recorded prospectively (graded according to the 'Common Terminology Criteria for Adverse Events' (CTCAE) version 4.0, dated May 2009).

These criteria will be shown descriptively in the safety analysis set.

The analyses of adverse events will be performed twice on the safety analysis set:

- by treatment group at inclusion;
- by group in which treatment was received at least once during the study. In this analysis, the AE will be attributed to ongoing treatment at the start of the AE. An AE beginning after a treatment was discontinued could be attributed to the treatment depending on the rules shown in the table below.

Prior to the safety analysis, the number of patients who received the treatment at least once in the group (targeted therapy/other treatments) and in the treatment subgroups will also be presented. Exposure for each treatment group and subgroup will be calculated.

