5.7.1. Treatment Drop-outs and Documented Reasons for Dropping Out of the Study

The following parameters will be presented for each of the analysis groups (targeted therapy or other treatment) and for each treatment:

- Total duration of exposure since starting treatment (also shown for the reference set).
- Numbers and percentages of patients who had at least one documented discontinuation of treatment in the study. The results will be shown for incident patients, prevalent patients and then for all patients.
- Number of documented temporary discontinuations by patient in the study.

- Time to the first temporary discontinuation from inclusion into the study. The results will be shown for incident patients, prevalent patients and then for all patients.
- Reasons for temporary discontinuations.
- Durations of temporary discontinuations.
- Numbers and percentages of patients who discontinued treatment permanently.
- Time until permanent discontinuation from inclusion into the study. The results will be shown for incident patients, prevalent patients and then for all patients.
- Time until permanent discontinuation from inclusion. Results will be shown for incident patients, prevalent patients and then for all patients.
- Reason for permanent discontinuation.

The analyses of exposure to treatment will be described by treatment received at inclusion but also by treatment received at least once during the study (main treatment or as a combination). If the patient takes the same treatment on several occasions over different periods, the sum of the exposure periods will be calculated.

The analyses of temporary discontinuations will be described by main treatment received at inclusion but also by main treatment ongoing at the time of temporary discontinuation.

In addition, the total duration of exposure of the treatment at inclusion since it was started will be analysed by the ECOG index value at inclusion.

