5.7.2. Adverse Events

The numbers and percentages of patients with the following characteristics will be shown overall, and by group at inclusion during the study (targeted therapy/other treatments). We will also show the results by treatment being received at the time of inclusion and during the study: everolimus/sunitinib/chemotherapy/somatostatin analogs etc.

- at least one adverse event,
- at least one serious adverse event,
- at least one adverse event with a suspected relationship with the study treatment,
- an adverse event which was fatal,
- at least one adverse event resulting in permanent discontinuation of treatment,
- at least one adverse event resulting in dosage adjustment/temporary discontinuation of treatment.

- at least one adverse event with a suspected relationship with the study treatment leading to permanent discontinuation of the treatment,
- at least one adverse event with a suspected relationship with the study treatment leading to a dosage adjustment/temporary discontinuation of treatment,
- at least one serious adverse event with a suspected relationship with the study treatment leading to permanent discontinuation of the treatment,
- at least one serious adverse event with a suspected relationship with the study treatment leading to a dosage adjustment/temporary discontinuation of treatment.

The same information will be produced for grade ≥ 3 adverse events.

The following information will also be shown:

- at least one grade 3 adverse event,
- at least one grade 3 serious adverse event,
- at least one grade 3 adverse event with a suspected relationship with the study treatment,
- at least serious grade 3 adverse event with a suspected relationship with the study treatment,
- at least one grade 4 or higher adverse event,
- at least one grade 4 or higher adverse event with a suspected relationship with the study treatment.

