NB: the listings will show the retrospective adverse events and the prospective adverse events, whereas the summary tables will only include the prospective adverse events.

The listing of adverse events reported in patients excluded from the safety analysis set will be provided where applicable.

Handling of missing data:

If the seriousness (serious/non-serious) and/or causality with the treatment are missing, the most adverse situation for treatment is assumed in the summary tables, i.e. a serious case and/or one related to the study treatment.

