9.4.2. Adverse Events

Programmer note: All of the tables below are shown:

- By treatment at inclusion: Targeted therapy/Other treatments (somatostatin analogs/chemotherapy /...)/ Total.
- By treatment at inclusion: Everolimus/Sunitinib/chemotherapy/somatostatin analogs/interferon alpha/somatostatin analog/metabolic radiotherapy/total.
- By treatment received at least once during the study: Targeted therapy/Other treatments (somatostatin analogs/chemotherapy/...).
- By treatment received at least once during the study: Everolimus/Sunitinib/chemotherapy /somatostatin analogs/interferon alpha/somatostatin analog/metabolic radiotherapy.

As a result, the summary tables will be duplicated.

Table 14.3.2.1: General Overview of Adverse Events – Safety Analysis Set

		Targeted therapies (N=XX)	•••	Total (N=XX)
At least one adverse event	N	XX (XX.X%)	XX (XX.X%)	XX (XX.X%)
Number of adverse events	N	XX	XX	XX
At least one serious adverse event	N	XX (XX.X%)	XX (XX.X%)	XX (XX.X%)
Number of serious adverse events	N	XX	XX	XX
At least one adverse event suspected to be related to the study treatment	N	XX (XX.X%)	XX (XX.X%)	XX (XX.X%)
Number of adverse events suspected to be related to the study treatment	N	XX	XX	XX
At least one adverse event resulting in death	N	XX (XX.X%)	XX (XX.X%)	XX (XX.X%)
Number of adverse events resulting in death	N	XX	XX	XX
At least one adverse event resulting in permanent discontinuation of treatment	N	XX (XX.X%)	XX (XX.X%)	XX (XX.X%)
Number of adverse events resulting in permanent discontinuation of treatment	N	XX	XX	XX
At least one adverse event leading to change in dosage/temporary discontinuation of treatment	N	XX (XX.X%)	XX (XX.X%)	XX (XX.X%)
Number of adverse events leading to change in dosage/temporary discontinuation of treatment	N	XX	XX	XX
At least one adverse event suspected to be related to the study treatment leading to permanent discontinuation of treatment	N	XX (XX.X%)	XX (XX.X%)	XX (XX.X%)

Table 14.3.2.1: General Overview of Adverse Events – Safety Analysis Set

		Targeted therapies (N=XX)		Total (N=XX)
Number of adverse events suspected to be related to the study treatment leading to permanent discontinuation of treatment	N	XX	XX	XX
At least one adverse event suspected to be related to the study treatment resulting in a change in dosage/temporary discontinuation of treatment	N	XX (XX.X%)	XX (XX.X%)	XX (XX.X%)

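### The adverse-event tables pool incident and prevalent patients over the post-inclusion period only, so their percentages are not adverse-event risks from treatment start

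*SAP*

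**What the plan says.** SAP 5.7.2 puts both retrospective and prospective events in the listings, "whereas the summary tables will only include the prospective adverse events". The population is the safety analysis set (SAP 5.7: "These criteria will be shown descriptively in the safety analysis set"). SAP 4.3.1 defines it as "all patients included in the study who received at least one dose of the documented treatment" and requires that a prevalent patient's treatment still be ongoing at inclusion. Incident and prevalent patients therefore share one denominator.

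The AE tables are broken down by treatment only. The programmer note in SAP 9.4.2 gives "By treatment at inclusion: Targeted therapy/Other treatments" and, as a second version, "By treatment received at least once during the study: Targeted therapy/Other treatments (somatostatin analogs/chemotherapy". The tables by system organ class and preferred term (SOC/PT) exist only in the second version. Neither SAP 5.7.2 nor the templates split AEs by incident or prevalent status.

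Other parts of the SAP do make the distinction:
- SAP 5.7.1, for having any discontinuation and for the times to temporary and permanent discontinuation: "The results will be shown for incident patients, prevalent patients and then for all patients".
- SAP 5.5.1 handles left truncation for overall and progression-free survival (OS and PFS) and adds a supportive analysis in incident patients.
- SAP 6.1.3 describes the truncation problem, but its remedy covers OS and PFS only. On AEs, the limitations in SAP 6.2 mention only combination treatments.

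For a patient already on treatment, AE notification starts at consent (Protocol section 7, notification period). Earlier AEs are collected only if clearly related to everolimus, in patients on everolimus, or to a Pfizer product (Protocol 5.2.2 and section 7; SAP 3.3, Table 1).

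**The concern.** A prevalent patient's first weeks or months on treatment contribute nothing to the AE tables. A patient who stopped early for toxicity could not be included as a prevalent patient on that line. One percentage thus averages two different quantities: risk from the first dose, and risk from some later point among those still on treatment. It estimates neither.

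Two consequences follow. A reader who takes the percentage as the risk facing someone starting the drug may be misled, in a direction that depends on when toxicity occurs. And because the tables place treatment groups side by side, a difference in prevalent share between groups can appear as a difference in toxicity.

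**Working it through.** **The plan's own figure.** SAP 4.2 gives the precision of a proportion. With half-width = 1.96 × √(p(1−p)/n) and p = 0.5, n = 150 gives 8.0 points and n = 75 gives 11.3, as printed. This is the yardstick for the effects below.

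**Inputs.** Follow-up of 24 months from inclusion is from the documents. They give no AE rate, AE timing, prevalent share or time from start to inclusion. Everything else is assumed:
- line length exponential with median 11 months, so μ = ln 2 / 11 = 0.063 per month;
- prevalent patients' treatment starts uniform over the previous 36 months, given that they are still on treatment at inclusion;
- AE hazard h₁ per month for the first 3 months, then h₂;
- events counted on the inclusion line only.

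**Formulas.** Let H(t) be the cumulative AE hazard. For a patient included a months after starting,

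R(a) = ∫ from a to a+24 of h(t) · exp{−[H(t) − H(a)] − μ(t − a)} dt.

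Incident risk is R(0). Prevalent risk is the average of R(a) over a from 0 to 36. The weight is exp(−μa − H(a)) for AEs that end treatment, since such patients are no longer there to be included. It is exp(−μa) for grade ≥3 AEs, which are assumed not to end the line. Pooled risk at half prevalent is the mean of the two.

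**Worked incident value**, h₁ = 0.08 and h₂ = 0.01:
- months 0–3: (0.08/0.143) × (1 − e^(−0.429)) = 0.195
- months 3–24: e^(−0.429) × (0.01/0.073) × (1 − e^(−1.533)) = 0.070
- total 0.265

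**Results (%)**

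| Assumed hazard per month | Incident | Prevalent | Pooled, half prevalent |
|---|---|---|---|
| AE stop, 0.04 then 0.01 | 18.2 | 12.2 | 15.2 |
| AE stop, 0.08 then 0.01 | 26.5 | 13.3 | 19.9 |
| Grade ≥3, 0.10–0.12 then 0.02–0.03 (four combinations) | 36–44 | 22–30 | 29–37 |
| AE stop, flat 0.02 | 20.8 | 20.8 | 20.8 |
| AE stop, 0.01 then 0.03 | 24.9 | 28.3 | 26.6 |

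The gap comes from the shape of the hazard. Early toxicity puts the pooled figure below the incident figure, a flat hazard removes the gap, and late toxicity puts it above.

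**Between groups.** Two groups with identical hazards, 30% and 70% prevalent, differ by (0.70 − 0.30) × (incident − prevalent). The smallest early-toxicity case gives 0.4 × (18.2 − 12.2) = 2.4 points. The largest (grade ≥3, 0.12 then 0.02) gives 0.4 × (39.2 − 22.8) = 6.6 points.

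**Precision if split**, assuming half prevalent:
- A group of 75 gives about 37 per column. The half-width is about 16 points at p = 0.5 and 13 at p = 0.2.
- A single targeted drug at its minimum of 35 gives about 17 per column, with half-widths of about 24 and 19 points.

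**The case against.** The strongest reply is that the tables do what the plan says. Protocol 8.3.2.1 and SAP 5.5 both define the safety analysis over the prospective period. In the by-treatment-received version, the denominator is patients who received the treatment during that period. This stands: the percentages are correct for that quantity.

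A reader might infer that the tables understate AE rates outright. The documents do not support that, because nothing in them says when AEs occur. For a fixed set of patients, post-inclusion events are a subset of events since start, so the tabulated figure cannot exceed their own since-start figure. Against 24-month risk in new starters, however, the direction depends on timing, and the last two rows of the table show no gap and the opposite gap.

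A reader might also infer that leaving pre-inclusion AEs out of the tables is itself the error. It is not. Their collection is selective and differs by drug, so tabulating them would add a drug-dependent bias. They remain visible in Listing 16.2.6, which flags prospective events.

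The between-group effect of 2–7 points is smaller than the SAP's half-width at n = 75 (9.1–11.3 points for proportions of 20–50%). Both documents call formal comparison inappropriate, and Table 14.1.3.1 already shows incident and prevalent counts by group. These points limit the harm but do not remove it: the counts do not let a reader recover separate AE percentages.

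Finally, the incident/prevalent flag describes only the line at inclusion. A prevalent patient's later lines are observed from their start, so applying the flag to the by-treatment-received or SOC/PT tables would misplace fully observed data. This stands and shapes the fix.

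**Conclusion.** The concern holds as a matter of interpretation and reporting. The AE tables pool two kinds of patient over the post-inclusion period, and the result should not be read as AE risk from treatment start. If toxicity is concentrated early, the pooled figure falls below the incident figure: by about 3–7 points for AE-related stopping (18.2 against 15.2; 26.5 against 19.9), and to 29–37% against 36–44% for grade ≥3. With a flat hazard there is no gap, and with late toxicity the pooled figure is higher. Unequal prevalent shares could create an apparent group difference of about 2–7 points at 30% against 70% under early toxicity. All these sizes rest on assumed hazards, line length and prevalent shares. What the documents do establish is the pooling, the restriction to prospective events and the absence of any split or warning for AEs.

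**What to change.** 1. In SAP 5.7.2 and 9.4.2, for the by-treatment-at-inclusion versions of Tables 14.3.2.1 and 14.3.2.2, add incident, prevalent and all columns within targeted therapies and within other treatments. Label the incident column as the estimate of AE risk from treatment start.
2. If the by-treatment-received and SOC/PT tables are also split, classify each treatment line by whether it started before inclusion or at/after inclusion, not by the patient's inclusion flag.
3. Keep retrospective AEs in the listings only.
4. Add a sentence to SAP 6.2 saying that the pooled AE percentages cover the prospective period only and are not risks from treatment start.

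The cost is extra columns from data already held; the flag is already tabulated by group in Table 14.1.3.1. The drawback is smaller denominators, so keep the pooled column and do not split by individual drug.

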5.7.3. Deaths

A listing of deaths describing the cause of death will be presented. All patients who died will be shown in this listing (including cases in which death is reported in the AEs after the end of the study).

5.8. Amendments from the Statistical Part of the Protocol

In the survival analysis, the 95% confidence intervals will be estimated using the Klein and Moeschberger equation.

5.9. Additional Analyses

5.9.1. Characteristics of Patients Based on having Received at Least One Targeted Therapy before Inclusion

The characteristics of patients will be described according to the "at least one targeted therapy before inclusion (yes/no)" subgroup in relation to the reference set.

Characteristics of interest are:

- Demographic characteristics,
- ECOG index,
- Comorbidities and history,
- Comorbidities and relevant history,
- Initial diagnosis of the disease,
- Characteristics of the pancreatic neuroendocrine tumour when starting the current line of treatment or line of treatment started at inclusion,

- Previous locoregional cancer treatments,
- Investigations performed most recently,
- Previous cancer treatment lines.

5.9.2. Time Between Diagnosis and Initiation of Ongoing Treatment at Inclusion for Metasynchronous Patients

The time (in years) between the date of diagnosis and initiation of ongoing treatment at inclusion will be presented for metasynchronous patients. A patient is considered as metasynchronous when a metastatic tumour was present at diagnosis.

5.9.3. Therapeutic Pathway of Patient

The therapeutic pathway of the patient will be described based on the three treatments (main treatment line: Targeted therapy, Chemotherapy and Somatostatin analogs).

Targeted therapy

The targeted therapy will be described for each period (overall follow-up, before inclusion, after inclusion) and as follows:

- Number of patients having received at least one targeted therapy.
- Number of patients having received Everolimus at least once.
- Number of patients having received Sunitinib at least once.
- Number of patients having received Pazopanib at least once.
- Number of patients having received Everolimus at least once and Sunitinib at least once.
- Number of patients having received Everolimus at least once, but not Sunitinib or Pazopanib.
- Number of patients having received Sunitinib at least once, but not Everolimus or Pazopanib.
- Number of patients who never received targeted therapy.
- Number of targeted therapies received per patient (quantitative and by class: 0 / 1 / 2 / 3 / 4 and more).

Targeted therapy will be described for the entire follow-up based on:

• Number of patients having received two different targeted therapies (Everolimus and Sunitinib, or Everolimus and Pazopanib).

In addition, the position of the targeted therapy in the care pathway of the patient will be described for the entire follow-up:

- Number of patients having received a targeted therapy as the 1st, 2nd, 3rd, nth main treatment line.
- Number of patients having received a targeted therapy immediately before/after chemotherapy.
- Number of patients having received a targeted therapy immediately before/after a somatostatin analog (as main treatment).

The duration of the targeted therapy (in months) and reasons for the discontinuation will also be described irrespective of the targeted therapy and by differentiating between Everolimus and Sunitinib during the period before inclusion then after inclusion.

The total duration of the targeted therapy (obtained by adding the periods before inclusion and after inclusion) will be described.

The analysis and duration of the targeted therapy (irrespective of the targeted therapy) and the reasons for the discontinuation will also be presented based on the following subgroups:

- Main treatment lines during follow-up (1/2/.../n).
- Number of patients with ≤ 2 lines, ≥ 2 main treatment lines for the entire follow-up.
- Ki67 (the most recent prior to inclusion) ($\leq 10\% / > 10\%$).
- Liver invasion at initiation of the ongoing treatment line or line started at inclusion $(\le 50\% / > 50\%)$.
- Number of metastatic sites when starting the current line of treatment or line of treatment started at inclusion (≤2 / >2). The "not reported" modality will be considered as missing data.

Chemotherapy

Chemotherapy will be described for each period (overall follow-up, before inclusion, after inclusion) and as follows:

- Number of patients having received chemotherapy at least once.
- Number of patients having never received chemotherapy.
- Number of chemotherapies received per patient (quantitative and by class: 0 / 1 / 2 / 3 / 4 and more).

• Number of patients having received chemotherapy and a somatostatin analog as main treatment.

In addition, the position of chemotherapy in the care pathway of the patient will be described for the entire follow-up:

- Number of patients having received chemotherapy as the 1st, 2nd, 3rd, nth main treatment line.
- Number of patients having received chemotherapy immediately before/after targeted therapy.
- Number of patients having received chemotherapy immediately before/after a somatostatin analog (as main treatment).
- Number of patients having received chemotherapy as 1st line at inclusion then targeted therapy as 2nd line (yes/no).
- Number of patients having received alkylating chemotherapy after inclusion (yes/no).
- Number of alkylating chemotherapies received after inclusion.

Alkylating agents are listed in Appendix 10.2.

Somatostatin analogs

Somatostatin analogs will be described for each period (entire follow-up, prior to inclusion, after inclusion) overall (main or combination treatment), if received as a main or combination treatment and as follows:

- Number of patients having received at least one somatostatin analog.
- Number of patients having never received a somatostatin analog.
- Number of somatostatin analogs received per patient (quantitative and by class: 0 / 1 / 2 / 3 / 4 and more).

In addition, the position of the somatostatin analog in the care pathway of patients will be described for the entire follow-up:

- Number of patients having received a somatostatin analog as the 1st, 2nd, 3rd, nth main treatment line.
- Number of patients having received a somatostatin analog in combination as the 1st, 2nd, 3rd, nth main treatment line.
- Number of patients having received a somatostatin analog as the 1st, 2nd, 3rd, nth main treatment line or in combination.

- Number of patients having received a somatostatin analog as the main treatment line immediately before/after targeted therapy.
- Number of patients having received a somatostatin analog as the main treatment line immediately before/after chemotherapy.

Surgery

Number and percentage of patients who underwent surgery are described for each period (entire follow-up, before inclusion, after inclusion). Surgery for primary, surgery for liver metastases and surgery recorded under "other treatment" will be considered.

